15 PUBLICATION POLICY

Results of this trial will be submitted for peer reviewed journal publication. Manuscript(s) will be prepared by the Trial Management Group. Authorship of the final manuscript(s), interim publications or abstracts will be in accordance with ICMJE authorship policy.

To maintain the scientific integrity of the trial, data will not be released prior to the end of the trial, either for trial publication or presentation purposes, without the permission of the Chief Investigator. Any secondary publications and presentations prepared by investigators must be submitted to the TMG in a timely fashion and in advance of being submitted for publication. Individual collaborators must not publish data concerning their patients which is directly relevant to the questions posed in the trial until the main results of the trial have been published.


29.	Scherber R, Dueck AC, Johansson P et al. The Myeloproliferative Neoplasm Symptom Assessment	
	$Form \ (MPN-SAF): International \ Prospective \ Validation \ and \ Reliability \ Trial \ in \ 402 \ patients. \ Blood \ 2011;$	
	118(2): 401-408	

APPENDIX 1: WORLD HEALTH ORGANISATION CRITERIA FOR THE DIAGNOSIS OF CHRONIC MYELOMONOCYTIC LEUKAEMIA (2008) (5)

A diagnosis of CMML requires the following to be present:

- 1) Persistent peripheral blood monocytosis >1x10⁹/l
- 2) No Philadelphia chromosome or BCR-ABL1 fusion gene
- 3) No rearrangement of *PDGFRA* or *PDGFRB* (should be specifically excluded in cases with eosionophilia)
- 4) Fewer than 20% blasts* in the blood and in the bone marrow
- 5) Dysplasia in one or more myeloid lineages. If myelodysplasia or absent or minimal, the diagnosis of CMML may still be made if requirements 1-4 are met, *and*:
 - an acquired, clonal cytogenetic or molecular gene abnormality is present in the haematopoietic cells, **or**
 - the monocytosis has persisted at least 3 months and
 - all other causes of monocytosis have been excluded.

(*Blasts include myeloblasts, monoblasts and promonocytes. Promonocytes are monocytic precursors with abundant light grey or slightly basophilic cytoplasm with few scattered, fine lilaccoloured granules, finely-distributed, stippled nuclear chromatin, variably prominent nucleoli, and delicate nuclear folding or creasing, and in this classification are equivalent to blasts. Abnormal monocytes which can be present both in the peripheral blood and bone marrow are excluded from the blast count.)

CMML is further subdivided into two sub-categories, depending on the number of blasts (plus promonocytes) found in the blood and bone marrow as follows:

CN	MML-1	Blasts (including promonocytes) <5% in the peripheral blood, <10% in the bone	
		marrow	
CI	MML-2	-2 Blasts (including promonocytes) 5-19% in the peripheral blood or 10-19% in the bo	
		marrow, or when Auer rods are present irrespective of the blast plus promonocyte	
		count	

WHO Classification of Tumours of Haematopoietic and Lymphoid Tissues (2008)

APPENDIX 2: CMML-SPECIFIC PROGNOSTIC SCORING SYSTEM (CPSS) (11)

	Variable scores		
Variable	0	1	2
WHO subtype	CMML-1	CMML-2	
	Blasts (including	Blasts (including	
	promonocytes) <5% in	promonocytes) 5-19% in	
	peripheral bloods and	peripheral blood and 10-	
	<10% in bone marrow)	19% in bone marrow or	
		presence of Auer rods	
FAB subtype	Myelodysplastic CMML	Myeloproliferative	
	(WBC <13 x10 ⁹ /l)	CMML	
		(WBC ≥13 x10 ⁹ /l)	
CMML-specific	Low risk	Intermediate risk	High risk
cytogenetic risk	(Normal; Isolated –Y)	(All other abnormalities)	(Trisomy 8; Complex
classification			karyotype [≥3
			abnormalities];
			Abnormalities of
			Chromosome 7)
Red cell transfusion	No	Yes	
dependency			

Overall Score	CPSS risk group
0	Low
1	Intermediate-1
2-3	Intermediate-2
4-5	High

- Neutrophils If pre-treatment neutrophils $\leq 0.5 \times 10^9/I$: increase to $> 0.5 \times 10^9/I$ (and by $\geq 100\%$)
 - If pre-treatment neutrophils 0.5-1.0 x 10^9 /I: an absolute increase of \geq 0.5 x 10^9 /I (and by at least 50%)
- **Spleen** either a minimum 50% reduction in palpable splenomegaly of a spleen that is a least 10cm palpable at baseline or a spleen that is palpable at more than 5cm at baseline becoming not palpable
- **Symptoms** improvement in symptoms as noted by a decrease of ≥50% in the MPN-SAF Total Symptom Score (only valid if baseline score>20)*

Disease Progression (requires a combination of either 2 major, 1 major & 2 minor, or 3 minor criteria from the list below)

Major Criteria of disease progression

Increase in bone marrow blast count: -<5% blasts: ≥50% increase (and to >5% blasts)

- 5-10% blasts: ≥50% increase (and to >10% blasts)

- 10-20% blasts: ≥50% increase (and to >20% blasts)

Evidence of cytogenetic evolution: - appearance of new cytogenetic abnormality

- increase in cytogenetic burden of disease by ≥50%

• New extramedullary disease: - worsening splenomegaly (either from previously inpalpable to

>5cm palpable, or >100% increase in previous 5-10cm

splenomegaly, or ≥50% increase in previous >10cm splenomegaly)

- extramedullary disease outside the spleen (including hepatomegaly, skin lesions, granulocytic sarcoma)

Minor Criteria of disease progression

- New transfusion dependence (at least 2u of red cells in the past month for Hb<85g/l that was not associated with clinically overt bleeding or felt to be associated with therapy
- Significant loss of maximal response of cytopenias: ≥50% decrement from maximum response in neutrophils or platelets (not felt to be associated with therapy)
- Reduction in Hb by 15g/l from best response or baseline (not felt to be associated with therapy)
- Increase in symptoms as noted by an increase of ≥50% in the MPN-SAF Total Symptom Score*
- Evidence of molecular clonal evolution

^{*} The use of the MPN-SAF Total Symptom Score within the International Consortium MDS/MPN Response Criteria is currently considered exploratory. Validation among patients within MDS/MPN is currently under way. (28)

APPENDIX 4: WATTEL ET AL RESPONSE CRITERIA IN CMML (14)

Clinical Remission

- Normal blood count: leukocytes $4 10 \times 10^9$ /l, monocytes $<1 \times 10^9$ /l, neutrophils $1.5 7 \times 10^9$ /l, platelets $>150 \times 10^9$ /l, haemoglobin >100 g/l (with no transfusion requirement)
- Normal bone marrow aspirate: blasts<5%, monocytes<5%, with absence of myelodysplastic features
- Normal bone marrow karyotype (if an abnormal clone was previously present)
- Absence of extramedullary leukaemia

Good Response

One of the following:

- Leukocytes $<10 \times 10^9$ /l and platelets $>100 \times 10^9$ /l and haemoglobin >100 g/l with no transfusion requirement and no extramedullary leukaemia
- Disappearance of prior visceral involvement (skin disease, pleural / pericardial / peritoneal effusion)
- In patients treated after progression to AML: reversion to chronic CMML phase

Minor Response

One of the following:

- >50% reduction of the leukocyte count and leukocytes <10 x10⁹/l
- >50% reduction of the transfusion requirement or increase in haemoglobin >20 g/l
- Doubling of the platelet count (if initially $>25 \times 10^9/I$) or increase by $> 50 \times 10^9/I$ (if initially $<100 \times 10^9/I$)
- Reduction in spleen size by more than 5cm
- Significant reduction (>50%) of cutaneous lesions or serous effusions

Progression

One of the following:

- Doubling of the leukocyte count (if initially >10 $\times 10^9$ /l), or increase by more than 10 $\times 10^9$ /l (if initially <10 $\times 10^9$ /l)
- Drop in haemoglobin >20 g/l or >50% increase in transfusion requirement
- >50% reduction in platelet count, if initially between 50-200 x10⁹/l
- Increase in spleen size by more than 5cm
- >10% increase in marrow blasts, or progression to AML
- Worsening (>50%) of cutaneous lesions or serous effusions

Stable Disease

All other disease situations

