5.1 Inclusion Criteria

Patients will be eligible for the MONOCLE study if **all** of the following apply:

1. Newly-diagnosed or previously-treated CMML meeting WHO criteria (Appendix 1) with the following characteristics:

All CMML-2 patients are eligible.

For patients classified as CMML-1, the following must be present:

· Symptomatic bone marrow failure or myeloproliferation defined as one or more of:

red cell transfusion dependence with pre-transfusion Hb <90g/I

symptomatic anaemia (Hb <115g/l)

thrombocytopenia (platelets <50 x 10⁹/l)

symptomatic bleeding due to platelet function defect or DIC/fibrinolysis

white blood cell count >50 x 109/l

and/or

· CMML-specific Prognostic Score (CPSS) of intermediate-2 or high risk (11) (see Appendix 2 for derivation of CPSS score)

and/or

- · Systemic symptoms including weight loss with no alternative explanation (10% of baseline weight within previous 6 months)
- · Symptomatic splenomegaly
- · Symptomatic extramedullary involvement, e.g. skin infiltration, serous effusions
- 2. Subject is able and willing to sign the Informed Consent Form
- 3. Age greater than or equal to 18 years at the time of signing the Informed Consent Form
- 4. Willingness to undergo scheduled assessments as per the study protocol including stipulated bone marrow assessments
- 5. ECOG performance status of 0-2 at study entry (see Appendix 6)
- 6. Women of childbearing potential must have a negative urine pregnancy test within 7 days prior to starting study drug

- 7. Women of childbearing potential must use at least two effective contraceptive methods throughout the study and for three months following the date of the last dose of study drug (see Appendix 7)
- 8. Men whose partner is a woman of childbearing potential must use at least two effective contraceptive methods (see Appendix 7)

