10.4.2 Secondary outcome measures

- Incidence of CR / PR / clinical benefit will be defined according to the International Consortium MDS/MPN Response Criteria⁽²⁸⁾ (see Appendix 3) at day 29 of the sixth or last cycle of tefinostat (whichever is the earlier). Duration of response will be measured from the date of investigations confirming the achievement of response until the date on which it is confirmed that the patient is no longer sustaining response.
- Overall clinical response rate according to Wattel and Modified IWG criteria (see Appendix 4 and 5).
 Responses will be defined as the cumulative proportion of patients achieving minor response of better (according to Wattel criteria⁽¹⁴⁾ and/or haematological improvement or better (according to the Modified IWG criteria)⁽²³⁾ at day 29 of the sixth or last cycle of tefinostat (whichever is the earliest).
- Red blood cell transfusion independence will be deemed to have been achieved if a patient who
 received red cell transfusion support in the eight weeks prior to baseline assessment remains free
 from red cell transfusion for a period of ≥ eight weeks
- Platelet transfusion independence will be deemed to have been achieved if a patient who received
 platelet transfusion support in the eight weeks prior to baseline assessment remains free from
 platelet transfusion for a period of ≥ eight weeks
- Overall survival is defined as the time from the date of trial registration to the date of death from any
 cause. Patients discontinuing the study, lost to follow-up or still alive at the end of study will be
 censored at the date of last follow-up.
- Progression-free survival is defined as the time from date of trial registration to the date of progression
 or death from CMML. Patients who die from a cause other than CMML prior to progression will be
 censored in the analysis. The date of progression is the date of the decision to investigate a clinical
 suspicion of progression which is subsequently confirmed.
- Time to AML transformation of CMML is defined as the time from trial registration to AML transformation of CMML or last follow-up. Patients in whom CMML does not transform to AML will be censored at the last date they were known to be alive and free from AML transformation of CMML. The date of AML transformation of CMML is the date of the decision to investigate clinical suspicion of AML transformation which is subsequently confirmed.

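### The count-based Wattel Good Response can already be met at entry, so an unchanged patient can count as a responder in this secondary rate

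*Protocol*

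**What the plan says.** Section 10.4.2 of the protocol makes the Wattel response rate a secondary outcome: "Responses will be defined as the cumulative proportion of patients achieving minor response of better", judged at the end of cycle 6 or of the last cycle if that comes sooner. It refers to Appendix 4 for the categories and sets no baseline condition of its own.

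In Appendix 4, Good Response needs "One of the following" from three routes. The first is a set of on-study values: leucocytes <10 x10⁹/l, platelets >100 x10⁹/l and "haemoglobin >100 g/l with no transfusion requirement and no extramedullary leukaemia". Minor Response also needs only one item, and its leucocyte item reads ">50% reduction of the leukocyte count and leukocytes <10 x10⁹/l". Stable Disease is whatever fits no other category.

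Section 5.1 states "All CMML-2 patients are eligible", with no condition on blood counts. CMML-1 patients can enter through "symptomatic anaemia (Hb <115g/l)", or through a CPSS of intermediate-2 or high alone.

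**The concern.** A response category should record something that happened after treatment began. The first Good Response route records only where the patient is at the assessment. Entry does not exclude patients who are already there, so stable disease with near-normal counts is scored as response. Stable Disease cannot reclaim such a patient, because it takes only those left over after the other categories.

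The leucocyte Minor Response does require a fall, but not from a raised count. A fall within the normal range, or below it, scores the same as control of a high count.

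The trial has one arm, so no comparator would show how many Wattel responders were merely unchanged. The reported rate is biased upwards by an amount that readers cannot see.

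**Working it through.** **1. The plan's own figures.** No target or expected value is given for the Wattel rate. The figures in section 10.1 concern the primary endpoints. An exact two-stage binomial calculation, with response and toxicity independent, uses stage 1 with at least 3 responses and at most 6 toxic of 19, and a final rule of at least 7 responses and at most 12 toxic of 40.

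- P(response rule met): 0.0801 at a 10% response rate and 0.9411 at 30%.
- P(toxicity rule met): 0.9108 at a 20% toxicity rate and 0.1028 at 40%.
- Accepting an ineffective drug: 0.0801 x 0.9108 = 0.073.
- Accepting a toxic drug: 0.9411 x 0.1028 = 0.097.
- Power: 0.9411 x 0.9108 = 0.857.

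These agree with the 10% bounds and 85% power. Nothing in them depends on Appendix 4.

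**2. Can an eligible patient be in Good Response at entry?** Apply section 5.1, Appendix 2 and Appendix 4 literally to patients with leucocytes 8 and platelets 150 x10⁹/l, no transfusion and no extramedullary disease, all unchanged at cycle 6:

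| Patient | Route into the trial | Category at cycle 6 |
|---|---|---|
| CMML-2, Hb 120 g/l | subtype alone | Good Response |
| CMML-1, symptomatic anaemia, Hb 110 g/l | Hb below 115 g/l | Good Response |
| CMML-1, trisomy 8, Hb 120 g/l | CPSS 0+0+2+0 = 2, intermediate-2 | Good Response |

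On the anaemia route the overlap is Hb above 100 and below 115 g/l.

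**3. Leucocyte Minor Response.** The test is (baseline − on-study)/baseline > 0.5 with an on-study count <10 x10⁹/l.

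- 30 to 9: 21/30 = 70% fall, a response as intended.
- 6 to 2.5: 3.5/6 = 58% fall, a response.
- 8 to 1.0: 7/8 = 88% fall, a response.

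Appendix 4's own Clinical Remission entry treats 4-10 x10⁹/l as normal, so the last two patients start normal and end below normal. The leucocyte item under Progression does depend on the starting count: "Doubling of the leukocyte count (if initially" is followed by a threshold.

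**4. Size.** Let f be the share of patients in the Good Response state at entry who stay in it, and t the true response rate among the others. The documents give neither; the values below are assumptions. The literal rate is f + (1 − f)t. With the baseline condition it is (1 − f)t if none of the entry-state patients responds through another item.

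| f | Unchanged responders of 40 | Literal rate, t = 0 | Literal rate, t = 10% | Conditioned rate, t = 10% |
|---|---|---|---|---|
| 5% | 2 | 5% | 14.5% | 9.5% |
| 10% | 4 | 10% | 19% | 9% |
| 20% | 8 | 20% | 28% | 8% |
| 30% | 12 | 30% | 37% | 7% |

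With t = 0 the conditioned rate is 0 of 40 throughout.

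**The case against.** **Appendix 4 is not without baseline conditions.** A reader might infer that it has none, unlike the modified IWG criteria in Appendix 5. The text does not support that. The platelet item sets starting thresholds (though doubling has no upper one), several Minor Response items are changes from a previous value, and the second Good Response route requires earlier visceral involvement. Complete Remission in Appendix 5 is also a pure state, although it adds marrow conditions. The point is confined to the count-based Good Response route and the leucocyte item.

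**The scale is published.** Appendix 4 cites a source that cannot be checked here, and cut-offs invented for this trial would make it a modified scale under the old name. This stands, and it limits the fix.

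**A patient who achieves a response might be taken to have newly reached it.** That is a fair reading of section 10.4.2, but nothing states it, and the residual definition of Stable Disease points the other way. A SAP may settle it; the protocol's definition as fixed does not.

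**Drug-induced leucopenia.** It is tempting to say that tefinostat toxicity will be counted as response. The reported phase I data do not support this: the related events listed in section 2.3.3 and Appendix 12 include no leucopenia, and Appendix 12 names creatinine and magnesium as the only potentially dose-related laboratory signals. Appendix 11 advises haematological monitoring, but from animal data. The drug targets monocytes, so part of a fall from a normal total count could be intended. Hydroxycarbamide is barred after cycle 3 (section 7.5), so it matters mainly for patients whose last cycle is one of the first three. The gap in the definition remains; its cause in any patient is open.

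**Low stakes.** The Wattel rate is descriptive (section 10.2), carries no decision rule, and is nowhere assigned the task of checking the primary rate. This stands.

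**Conclusion.** The point holds in a limited form. Read literally, Appendix 4 with section 10.4.2 scores some eligible patients with unchanged disease as Wattel responders, and also counts leucocyte falls from a count that was never raised. The direction is upwards.

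The size is unknown. A patient must meet all five conditions at entry and still meet them at assessment, and CMML-1 patients who enter with platelets <50 x10⁹/l, leucocytes >50 x10⁹/l, transfusion dependence or extramedullary involvement do not meet them at entry. The 2 to 12 of 40 follows from an assumed 5% to 30%, not from the documents.

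A reader might infer that the primary result is compromised. It is not: the primary response rate (section 10.4.1) and the stage 1 benefit rule (sections 8.3 and 10.1) use the International Consortium criteria, and no sample size, error rate or go/no-go threshold changes. This is a correction to one secondary definition.

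**What to change.** Add to section 10.4.2:

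- The count-based Good Response counts only if the patient did not already meet it at baseline. Name the pre-treatment count that applies, since blood is taken at screening and on day 1.
- Patients who met it at baseline stay in the denominator and can still respond through any other Wattel item.
- Report the literal Wattel rate alongside, for comparability with published results. Give the number of responders who already met the category at baseline, and the number whose only response is a leucocyte fall from a baseline below 10 x10⁹/l.

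Do not add new leucocyte or platelet cut-offs under the Wattel name. The leucocyte item stays as written, and the last count shows how much it matters.

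The cost is one paragraph. The baseline counts, transfusion history and examination findings needed are already collected (sections 8.1.1, 8.1.2 and 8.1.5). The secondary rate may be slightly lower, and two rates are shown instead of one. Entry-state patients with no other item open to them count as non-responders, which pulls the conditioned rate down somewhat; showing both rates makes this visible.

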APPENDIX 5: MODIFIED IWG RESPONSE CRITERIA IN MYELODYSPLASIA (23)

Complete Remission

- Bone marrow ≤5% myeloblasts with normal maturation of all cell lines
- Peripheral blood: Hb ≥110 g/l, Platelets ≥100 x10⁹/l, Neutrophils ≥1.0 x10⁹/l, No blasts

Partial Remission

 All CR criteria required except: bone marrow blasts decreased by ≥50% compared to pre-treatment, but still >5%. Bone marrow cellularity and morphology not relevant.

Haematologic Improvement†

Erythroid Response (if pre-treatment* Hb <110 g/l)

- Hb increase by 15 g/l
- Reduction in red cell transfusions by an absolute number of 4 units per 8 weeks compared with the pre-treatment transfusion number in the previous 8 weeks

Platelet Response (if pre-treatment* platelets <100 x109/l)

- If baseline count >20 x10⁹/l: an absolute increase of ≥30 x10⁹/l
- If baseline count <20 x 10⁹/l: an increase to >20 x10⁹/l, and by at least 100%

Neutrophil Response (if pre-treatment* neutrophils <1.0 x10⁹/l)

At least 100% increase and an absolute increase of >0.5 x10⁹/l

Stable Disease

• Failure to achieve at least PR/HI but no evidence of progression

Progressive Disease

• For patients with: <5% blasts: ≥50% increase in blasts to >5% blasts

5-10% blasts: ≥50% increase to >10% blasts

10-20% blasts: ≥50% increase to >20% blasts

- At least 50% decrement from maximum response in neutrophils / platelets
- Reduction in Hb by ≥20 g/l
- New transfusion dependence

*Pre-treatment counts should be averages of at least 2 measurements (not influenced by transfusions) and ≥1 week apart

†Responses must last at least 8 weeks

APPENDIX 6: ECOG PERFORMANCE SCALE (27)

Grade	Activity Performance Description
0	Fully active, able to carry out all pre-disease performance without restriction.
1	Restricted in physically strenuous activity but ambulatory and able to carry out work of a light or sedentary nature, eg. light house work, office work.
2	Ambulatory and capable of all self-care but unable to carry out any work activities. Up and about more than 50% of waking hours.
3	Capable of only limited self-care, confined to bed or chair more than 50% of waking hours.
4	Completely disabled. Cannot carry out any self-care. Totally confined to bed or chair.

APPENDIX 7: CONTRACEPTIVE METHODS

Female subjects

A 'woman of childbearing potential' (WCBP) is defined as:

• A sexually mature woman (ie. Any female who has ever experienced menstrual bleeding)

and

 Who has not undergone a hysterectomy or who has not been postmenopausal for at least 24 consecutive months (ie. Who has had menses at any time within the preceding 24 consecutive months)

WCBP must agree to use at least 2 effective contraceptive methods throughout the study and for 3 months following the date of the last dose of study drug.

The following are considered effective methods of contraception for WCBP:

- Contraceptive implant
- Levonorgestrel-releasing intrauterine system (IUS)
- Medroxyprogersterone acetate depot
- Tubal sterilisation
- Sexual intercourse with a vasectomised male partner only (vasectomy must be confirmed by 2 negative semen analyses)
- Ovulation inhibitory progesterone-only pills (ie. Desogestrel)
- Condoms and spermicidal jelly or Diaphragm and spermicidal jelly

Combined oral contraceptive pills are not recommended. Subjects using combined oral contraception should switch to one of the methods above. The increased risk of VTE continues for 4-6 weeks after stopping oral contraception

Male subjects

The following are considered effective methods of contraception for male subjects:

- Condoms and spermicidal jelly throughout study drug therapy, during any dose interruption and for to 3 months after cessation of study therapy if their partner is of childbearing potential
- Female partners must also use a method from the list above

